#### **4. Follow-up and surveillance**

1. Physical activity: It will be evaluated by means of the international physical activity questionnaire (IPAQ) that categorizes the levels of physical activity in: low (category 1), moderate (category 2) and high (category 3) according to the intensity, frequency and duration of the training. The recommendation will be made not to modify the usual training plan.
2. Nutritional plan: The monitoring will be carried out in a personalized way through a monthly face-to-face nutritional consultation.
3. Pharmacological treatment: The adherence to the pharmacological treatment will be monitored through a monthly telephone interview. Telephone assistance will be available to resolve doubts and report adverse effects.

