metabolic disorders such as diabetes and obesity, which are commonly present in patients with MAFLD. It has been demonstrated that the administration of 1200 mg of alpha-lipoic acid in patients with fatty liver disease reduces insulin resistance and serum leptin levels while increasing adiponectin concentration. However, it did not influence liver histology and biochemical markers. 

Therefore, our objective is to demonstrate that the administration of the combination of alpha-lipoic acid and Silybum marianum (LUDLEV®) can improve steatosis in patients with MAFLD when associated with a Mediterranean-style diet, while ensuring a favorable safety profile.

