## **OBJECTIVES**

### **Overall objective:**

To evaluate the effects of administering alpha-lipoic acid and Silybum marianum (LUDLEV® 300 mg/46.2 mg) in combination with a Mediterranean diet compared to

placebo plus a Mediterranean diet on fibrosis and steatosis in patients with MAFLD after 24 weeks of treatment.

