**Elimination criteria:**

- Patients who do not comply with the follow-up time and drug administration.
- Patients who do not comply with proper drug intake.
- Patients with intolerance or severe adverse effects to the components of the drug.
- Patients who are unable to undergo FibroScan® examination due to technical limitations.

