## 1. Initial assessment and follow-up

Initial medical assessment including:

1. Complete medical history
2. Hepatic ultrasound showing evidence of hepatic steatosis. The degree of hepatic steatosis will be determined according to Hamaguchi score ( $\geq 3$  points) classifying it as follows: absent (0 points), mild (1 point), moderate (2 points) and severe (3 points). This scoring system has a maximum sum of 6 points and considers hepatorenal echo contrast, hepatic brightness, deep attenuation and vascular visualization with a specificity of 100% and sensitivity of 91.7%.
3. The risk of fibrosis will be determined according to FIB-4, NAFLD score or APRI. FIB-4 is considered high risk of fibrosis score  $\geq 3.25$ , indeterminate 1.45-3.25 and absent  $\leq 1.45$ ; in NAFLD score high risk with  $\geq 0.675$ , indeterminate -1.455 to 0.675 and absent  $\leq -1.455$ ; in APRI high risk of significant fibrosis with score  $\geq 1.5$ , indeterminate 0.5-1.5 and absent  $\leq 0.5$ .
4. Transitional liver elastography with FibroScan® will be performed at baseline, 12 and 24 weeks follow-up to estimate hepatic fatty infiltration according to the controlled attenuation parameter (CAP) and hepatic stiffness in kilopascals (kpa). Considering fibrosis stages the following cut-off points F0  $\leq 6.4$ kpa, F1 6.5 to 6.9 kpa, F2 7 to 8.6kpa, F3 8.7 to 10kpa, F3-F4 10.1 to 15 kpa and F4  $\geq 15$ kpa. For hepatic fatty infiltration is considered by CAP S0  $\leq 247$ , S1 between 248 to 267, S2 268 to 279 and S3  $\geq 280$ . 10 representative valid measurements with success rate (IQR) 30% are considered. All measurements will be taken by the same operator.
5. At baseline, 12 and 24 weeks follow-up the following laboratory studies will be performed: blood biometry, blood chemistry, liver function tests, lipid profile and C-reactive protein, serum insulin, HOMA calculation.
6. The study of viral hepatitis type B and C will be performed at the beginning of the study.

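### A favourable safety profile is part of the stated aim, but the only reporting route named for adverse effects is a help line, so symptomatic events rest largely on spontaneous reports

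*Protocol*

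**What the plan says.** The Background closes with the aim of improving steatosis "while ensuring a favorable safety profile". The formal objectives do not take this up. The overall objective compares the active combination plus diet with "placebo plus a Mediterranean diet on fibrosis and steatosis in patients with MAFLD after 24 weeks of treatment". The specific objectives add biochemistry, weight and body composition, but not safety or tolerability.

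Adverse effects appear in two places. Section 4 (Follow-up and surveillance), item 3, says "Telephone assistance will be available to resolve doubts and report adverse effects". The Elimination criteria list "Patients with intolerance or severe adverse effects to the components of the drug", without saying how these patients are identified or how their events are reported.

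Every patient has these scheduled contacts:
- A monthly call: "The adherence to the pharmacological treatment will be monitored through a monthly telephone interview" (section 4, item 3).
- A monthly visit: dietary monitoring is done "through a monthly face-to-face nutritional consultation" (section 4, item 2).
- Laboratory tests at baseline, 12 and 24 weeks: "blood biometry, blood chemistry, liver function tests, lipid profile and C-reactive protein, serum insulin, HOMA calculation" (section 1, item 5).
- Medical follow-up at 12 and 24 weeks (Schedule of activities).

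None of these is described as including a question about adverse effects, and the laboratory tests are not described as safety monitoring.

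**The concern.** A help line records what patients decide to report. Mild or moderate symptoms that a patient does not link to the capsules, or does not think worth a call, tend to go unrecorded. In a trial of 50 patients each arm can expect only a handful of events of any one kind, so losing some of them can turn a visible signal into an empty row. A reader who knows that the trial set out to show a favourable safety profile could take that empty row as evidence of safety when it partly reflects the collection method.

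How adverse effects are elicited is a matter of data collection, which the protocol fixes. No analysis plan can later recover symptoms that nobody asked about. There is also a simple participant-safety interest in hearing of problems early.

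**Working it through.** The protocol states no safety figure, so there is nothing to reproduce. The check compares the text on each contact and then illustrates the size.

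**Step 1: the stated purpose of each contact.**

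| Contact | Frequency | Stated purpose | Adverse-effect enquiry stated? |
|---|---|---|---|
| Telephone assistance | When used | Doubts, adverse effects | Yes, but available on request |
| Telephone interview | Monthly | Drug adherence | No |
| In-person consultation | Monthly | Nutrition | No |
| Laboratory tests | Baseline, 12, 24 weeks | Follow-up measurements | No, but can reveal laboratory abnormalities |
| Medical follow-up | 12, 24 weeks | Follow-up and compliance | No, but may reveal some events |

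Symptomatic events between the 12- and 24-week assessments therefore have one named route, and the patient must use it.

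**Step 2: inputs for the illustration.**
- n = 25 per arm: 50 patients (Sample size calculation) randomised 1:1 (Interventions).
- True risk p on active treatment = 10%: an assumption.
- Capture fraction c, the share of true events that get recorded: an assumption, shown over a range. Full capture (c = 1) is the ideal; routine questioning approaches it but does not guarantee it.

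**Step 3: chance of recording no event in one arm**, P(0) = (1 − p × c)^25:
- c = 100%: 0.90^25 = 0.072, or 7%
- c = 60%: 0.94^25 = 0.213, or 21%
- c = 40%: 0.96^25 = 0.360, or 36%
- c = 30%: 0.97^25 = 0.467, or 47%

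**Step 4: what zero recorded events would then mean.** The one-sided 95% upper limit for the true risk after 0 of 25 is (1 − 0.05^(1/25)) / c:
- c = 100%: 11.3%
- c = 75%: 15.1%
- c = 50%: 22.6%
- c = 25%: 45.2%

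**Step 5: equal loss in both arms still hides a difference.** Take assumed true risks of 30% and 10%, each multiplied by the same c, with 25 per arm and a two-sided 5% normal-approximation test of two proportions. Power is 42% at full capture, 31% at 75%, 21% at 50% and 12% at 25%. For example, at 50% capture the recorded risks are 15% and 5%. No difference in reporting between arms is needed for this loss.

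**The case against.** The protocol does not say that the help line is the sole means of detecting adverse effects. Blood counts, blood chemistry and liver tests are taken from everyone at 12 and 24 weeks, medical follow-up takes place at the same times, and staff see or speak to each patient monthly. The interview is described by its purpose; its questions are not listed, so adverse effects may in practice be raised. The elimination criterion presupposes that someone identifies intolerance. This stands, and it limits the point: the document names one reporting route and states no routine enquiry, but it does not exclude other detection.

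A reader might also infer that under-reporting would differ between arms. The documents give no support for this. The trial is described as double-blind with a placebo, and no mechanism is apparent by which blinded patients would call at different rates by arm.

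A reader might further infer that the events of eliminated patients vanish from the data. The Elimination criteria do not say so. An event that leads to elimination must have been noticed, and which patients enter a safety table may be settled in an analysis plan that is not shown.

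Finally, safety appears only in one clause of the Background, the 10% risk and capture rates are assumptions, and 0 of 25 leaves an upper limit of 11.3% even with full capture. All of this is true. Better questioning will not make a trial of this size conclusive on safety. It removes an avoidable loss on top of that limit.

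**Conclusion.** The point holds in a limited form. The protocol claims an interest in a favourable safety profile, has no matching objective, and names only patient-initiated telephone contact for reporting adverse effects, while two monthly contacts with every patient are described for other purposes. The likely consequence is that absolute rates of symptomatic events are understated in both arms and a true difference is harder to detect. The documents do not show a bias between arms, nor that laboratory abnormalities or the events of eliminated patients are lost.

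The size depends on assumptions about risk and capture that the protocol does not supply. Under a 10% true risk and 25 per arm, the chance of a blank record moves from 7% at full capture to between 21% and 47% when 60% to 30% of events are captured. This does not touch the efficacy comparison. It is an inexpensive improvement that should be made if any safety statement is to be drawn from the trial.

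**What to change.** 1. In section 4 (Follow-up and surveillance), item 3, state that the monthly telephone interview asks every patient the same fixed adverse-effect questions, by staff blind to arm, and that the answers are recorded. Do the same at the monthly in-person visit. Keep the help line as an addition.
2. Add a safety objective to the specific objectives: adverse effects, and the laboratory tests already scheduled at 12 and 24 weeks, reported by arm.
3. State that patients who meet the elimination criteria still count in that report. This concerns reporting only and leaves clinical management as it is.

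The choice of intervals and the exact safety population can be left to the analysis plan.

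The cost is a few minutes per existing contact, one case-report page and one table, with no extra visits, tests or patients. The downside is that more minor events will be recorded in both arms.

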#### **5. Analysis of the results**

The analysis of the results, elaboration of figures and tables will be carried out with the statistical program IBS SPSS version 22.0. Nominal and ordinal variables will be described with frequencies and percentages; continuous and discrete variables with measures of central tendency and dispersion according to their distribution. The normality of data distribution will be evaluated with the Kolmogorov-Smirnov test, and nonparametric statistics will be used to evaluate intergroup differences between nominal variables. Non-parametric statistics will be used for ordinal variables. A p-value of less than 0.05 will be considered statistically significant.

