## **HYPOTHESIS**

The administration of the combination of alpha-lipoic acid and Silybum marianum (LUDLEV®) in combination with a Mediterranean diet reduces the degree of fibrosis and steatosis in patients with MAFLD as assessed by kPa and CAP measurements after 24 weeks of treatment.

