### **Specific Objectives:**

- To assess the effects of administering alpha-lipoic acid and Silybum marianum (LUDLEV® 300 mg/46.2 mg) in combination with a Mediterranean diet versus placebo plus a Mediterranean diet on fibrosis and steatosis in patients with MAFLD after 12 weeks of treatment.
- To evaluate changes in fibrosis measured by kPa using FibroScan® elastography after 12 and 24 weeks of administering alpha-lipoic acid and Silybum marianum (LUDLEV® 300 mg/46.2 mg) every 12 hours in combination with a Mediterranean diet, compared to placebo plus a Mediterranean diet in patients with MAFLD.
- To assess changes in the controlled attenuation parameter (CAP) measured by FibroScan® elastography after 12 and 24 weeks of administering alpha-lipoic acid and silybum marianum (LUDLEV® 300 mg/46.2 mg) every 12 hours in combination with a Mediterranean diet, compared to placebo plus a Mediterranean diet in patients with MAFLD.
- To evaluate biochemical improvement after 12 and 24 weeks of administering alpha-lipoic acid and Silybum marianum (LUDLEV® 300 mg/46.2 mg) every 12 hours in combination with a Mediterranean diet, compared to placebo plus a Mediterranean diet in patients with MAFLD.
- To assess weight loss and changes in body composition after 12 and 24 weeks of administering alpha-lipoic acid and Silybum marianum (LUDLEV® 300 mg/46.2 mg) every 12 hours in combination with a Mediterranean diet, compared to a Mediterranean diet alone in patients with MAFLD.

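### The analysis section assigns its tests to nominal and ordinal variables and gives continuous ones description only, although the hypothesis rests on CAP and kPa; no reading uses the baseline values already collected

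*Protocol*

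**What the plan says.** The Hypothesis section expects a reduction in fibrosis and steatosis "as assessed by kPa and CAP measurements after 24 weeks of treatment". The Specific Objectives ask for between-arm comparisons of measured quantities: "To evaluate changes in fibrosis measured by kPa using FibroScan® elastography after 12 and 24 weeks", "To assess changes in the controlled attenuation parameter (CAP) measured by FibroScan® elastography after 12 and 24 weeks", biochemical improvement at the same times, and "To assess weight loss and changes in body composition after 12 and 24 weeks of administering".

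Section 1 of the Interventions part (Initial assessment and follow-up) schedules FibroScan and laboratory tests at baseline, week 12 and week 24. It also gives cut-offs that turn CAP into S grades and kPa into F stages.

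Section 5 (Analysis of the results) is the only analysis text. It describes "continuous and discrete variables with measures of central tendency and dispersion according to their distribution" and checks normality with the Kolmogorov-Smirnov test. In the same sentence as that check it says that "nonparametric statistics will be used to evaluate intergroup differences between nominal variables". It then adds: "Non-parametric statistics will be used for ordinal variables". The significance threshold is 0.05. No between-group comparison, model or effect estimate is attached to a continuous variable, and no covariate is mentioned.

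**The concern.** Section 5 sorts variables into types and gives each type a treatment. The type that the hypothesis depends on receives summary statistics and nothing else, while the tests go to the other types. This goes beyond leaving detail to a statistical analysis plan: the protocol states a rule, and the rule as worded misses the main variables. A later plan would have to contradict it or guess what was meant.

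The possible meanings are different analyses: a rank test on week-24 values, a rank test on change, or a test on grades. With 20 patients per arm expected after losses, they can differ clearly in power. If the choice stays open until data are in hand, it can be made with knowledge of the results. The baseline readings that could sharpen the comparison are collected anyway, but no reading of section 5 uses them as a covariate.

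**Working it through.** The plan has no figure of its own on this point, so the check is first textual and then a comparison of the candidate analyses.

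**Step 1: outcomes against the tests assigned.**

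| Outcome in hypothesis or objectives | Type as measured | Grades defined in the protocol? | Between-group test in section 5 |
|---|---|---|---|
| CAP | continuous | yes, S0 to S3 | none as a measurement; ordinal sentence if graded |
| kPa | continuous | yes, F0 to F4 | none as a measurement; ordinal sentence if graded |
| Weight, body composition | continuous | no | none |
| Laboratory values | continuous | no | none |

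**Step 2: two readings that would repair the text.**

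- *Nominal* stands for *numerical*. A normality check has no purpose for nominal data, so this is plausible. It yields a rank test, but whether on week-24 values or on change is not said.
- CAP and kPa are analysed as grades under the ordinal sentence. This leaves the last two rows of the table without a test. It is also coarse. The cut-offs "S1 between 248 to 267, S2 268 to 279 and S3" (280 and above) make S1 267 − 248 + 1 = 20 units wide and S2 279 − 268 + 1 = 12 units wide, with S3 open-ended. A fall within S3 does not register. If mean CAP were 280 to 320 with SD 40 (assumed), the share of placebo patients in S3 would be Φ((mean − 280)/40), that is Φ(0) = 50% to Φ(1) = 84%.

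**Step 3: what baseline adjustment is worth.** Let r be the correlation between baseline and week 24, with equal SDs at both times. The protocol does not give r; 0.3 to 0.8 is assumed. Variance relative to week-24 values alone is 1 for week 24, 2(1 − r) for change and 1 − r² for the adjusted model. The ratio of adjusted to change is (1 + r)/2.

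| r | Change, 2(1 − r) | Adjusted, 1 − r² | Adjusted/change, (1 + r)/2 |
|---|---|---|---|
| 0.3 | 1.40 | 0.91 | 0.65 |
| 0.5 | 1.00 | 0.75 | 0.75 |
| 0.8 | 0.40 | 0.36 | 0.90 |

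Adjustment therefore lowers the variance by 9% to 64% against week-24 values, and by 35% (r = 0.3) to 10% (r = 0.8) against change.

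In detectable differences (20 per arm, two-sided 0.05, 80% power, noncentral t), week-24 values alone need 0.91 SD. At r = 0.5 the adjusted model needs 0.80 SD, allowing for the estimated covariate with a variance factor of 1 + 1/(2·20 − 4) and 37 degrees of freedom.

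**Step 4: power of the candidate analyses by simulation.** 20 per arm, two-sided 0.05, normal data, assumed true effect 0.7 SD:

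| Analysis | r = 0.3 | r = 0.5 | r = 0.8 |
|---|---|---|---|
| Rank test, week-24 values | about 55% | about 55% | about 55% |
| Rank test, change | 43% | 55% | 91% |
| Linear model with baseline | 61% | 69% | 94% |

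A rank test on the week-24 S grade reached 37% to 50% (mean CAP 280 to 320, SD 40).

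**Step 5: sensitivity to normality.** With heavy-tailed data (t with 3 degrees of freedom, scaled to unit variance; also an assumption) the order changes. At r = 0.3 the week-24 rank test has about 77% against 70% for the linear model. At r = 0.5 they are about equal. At r = 0.8 the rank test on change has about 98% against 94%.

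**The case against.** Four arguments weigh against the point.

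- **Slip of wording.** *Nominal* is most likely a slip for *numerical*, and the rank test it then describes is valid. This stands. A reader might infer that the protocol has no usable test for its hypothesis; the text does not support that. What remains is that the correction is not on the page and that the repaired sentence still does not say which values are ranked.
- **Covariates belong in the analysis plan.** Also right as far as it goes. A reader might infer that silence about the baseline is an error in itself. It is not: a protocol may leave that to the statistical analysis plan, which is not shown here. The baseline matters because section 5 needs rewriting anyway and the values are already scheduled.
- **A graded outcome may be intended.** The hypothesis speaks of the degree of fibrosis and steatosis, and the sample size rests on 70% versus 15% with a decrease in ultrasound-graded steatosis, a categorical outcome. This gives the grade reading real support. It does not cover weight, body composition or laboratory values, and the hypothesis names kPa and CAP measurements.
- **The power gain depends on assumptions.** True. A reader might infer from the normal-data figures that the linear model is always the stronger choice. Step 5 shows that it is not, and at high r its advantage over a rank test on change is small even under normality (94% versus 91%).

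**Conclusion.** The point holds as a fault of wording with a practical consequence. Section 5 assigns its tests to nominal and ordinal variables and only describes the continuous ones, so the rule as written misses CAP and kPa as measurements and every other continuous objective. The most probable intended meaning is a valid, unadjusted rank test; the grade reading is partial and loses information. Neither uses the baseline values as a covariate.

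The wording fault is certain but has no size of its own. The gain from adjustment, 9% to 64% of variance against week-24 values and 10% to 35% against change, rests on assumed r of 0.3 to 0.8 and equal SDs. The power figures further assume normality and an effect of 0.7 SD, none of which the protocol gives. They show that the candidate analyses differ at this sample size. They do not predict this trial's power.

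**What to change.** Rewrite section 5 so that continuous outcomes have a stated between-group comparison, and make it baseline-adjusted. Possible text:

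*Week-24 CAP and week-24 kPa are each compared between arms by a linear model with treatment and the baseline value. If kPa is skewed it is log-transformed; the scale is fixed in advance. The treatment effect is reported with a 95% CI, as a difference, or as a ratio where the log scale is used. A pre-specified rank-based analysis (on change from baseline, or a rank ANCOVA) is the sensitivity analysis. Week 12, weight, body composition and laboratory values are analysed in the same way.*

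Choose one of the two rank-based options beforehand. If S and F grades are also to be compared, say so and keep the ordinal sentence for them.

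Cost: no new visit, measurement or patient, and one degree of freedom per model. It is more than a correction of spelling, because it moves the main comparison from a rank test to a linear model. With heavy-tailed data that model can have less power, which is the reason for keeping the rank-based analysis. If the sponsor prefers to stay with rank tests, the minimum is to correct *nominal* and to say whether week-24 values or changes are compared.
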